10.4.4 Safety Analyses

Safety endpoints will assess adverse event rate (defined as the proportion of patients showing each type of adverse event or any adverse event). The severity and causality of all adverse events will be graded according to the new adverse event classification by the Society of Interventional Radiology Standards of Practice Committee [30].

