3.2 Secondary Objectives

The secondary objectives of the study are to determine whether genicular artery embolization is effective in improving

1. Knee pain using an electronic VAS at 1-, 3-, and 12-months (and final 18-48 months visit) post intervention
2. Knee pain using WOMAN pain score at 1- and 12-months (and final 18-48 months visit) post intervention
3. Knee stiffness using the WOMAC knee stiffness score at 1-, 3-, and 12- months (and final 18-48 months visit) post intervention
4. Physical function using the WOMAC function score at 1-, 3-, and 12- months (and final 18-48 months visit) post intervention
5. Self-reported quality of life using EQ-5D-5L scale at 1-, 3-, and 12- months (and final 18-48 months visit) post intervention [28]
6. Synovitis on MRI at 3 months post intervention

Other secondary objectives are to assess

1. Feasibility / technical success defined as successful selective catheterization of target vessel(s) and embolization from at least one feeding artery of the knee joint (with the embolization endpoint defined as suppression or reduction in the filling of (and therefore blood flow in) abnormal vessels visible on angiography).
2. Reduction in frequency of pain medication usage over 30-day period assessed at baseline and at 1, 3, and 12 months follow-up visits post intervention (acetaminophen, over the counter NSAIDs, prescription NSAIDs, opioids)
3. Reduction in frequency of knee injection therapy over 12-month period (assessed at baseline and at 12-month follow-up visit post intervention)
4. Reduction in frequency of need for physical therapy over 12-month period (assessed at baseline and at 12-month follow-up visit post intervention)
5. Safety evaluated by cumulative rates of adverse events (AE), as well as type and severity of each adverse event.

4 Study Design and Endpoints

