5.7 Participant Withdrawal or Termination

5.7.1 Reasons for Withdrawal or Termination

Participants are free to withdraw from participation in the study at any time upon request. Participation of a patient in this clinical study may be discontinued for any of the following reasons:

- The patient withdraws consent or requests discontinuation from the study for any reason;
- Occurrence of any medical condition or circumstance that exposes the patient to substantial risk and/or does not allow the patient to adhere to the requirements of the protocol;
- Any AE, clinically significant adverse event, severe laboratory abnormality, intercurrent illness, or other medical condition that indicates to the investigator that continued participation is not in the best interest of the patient;
- Pregnancy during study period;

CONFIDENTIAL

- Patient failure to comply with protocol requirements or study-related procedures;
- Termination of the study by the Sponsor, the regulatory authority, FDA, or IRB.
- The participant meets an exclusion criterion (either newly developed or not previously recognized) that precludes further study participation
- Progression of osteoarthritis requiring surgical therapy
- Patients found to have osteonecrosis on pre-procedural MRI

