5.7.2 Handling of Participant Withdrawals or Termination

If a patient withdraws prematurely from the study due to the above criteria or any other reason, study staff should make every effort to complete the full panel of assessments scheduled for the follow-up visits. The reason for patient withdrawal must be documented in the electronic case report form (eCRF). In the case of loss of follow-up, attempts to contact the patient will be made and documented in the patient's medical records. Every effort will be made to undertake protocol-specified safety follow-up procedures to capture AEs, serious adverse events (SAEs), and unanticipated problems (UPs).

Withdrawn patients can be replaced.

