10.3 Analysis Datasets

Participants who complete all follow-up visits will be included in the study.

CONFIDENTIAL

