10.4.3 Analysis of the Secondary Endpoint(s)

Analysis of secondary endpoints include: (1) changes in the mean WOMAC and VAS pain scores, the mean WOMAC knee stiffness and physical function scores and the total WOMAC knee physical function score; (2) the technical success rate (defined as the proportion of patients for whom the procedure was successfully completed); (3) the adverse event rate (defined as the proportion of patients showing each type of adverse event or any adverse event); (4) reduction in the usage of pain medication, the frequency of infection therapy, the need for physical therapy; and (5) the proportion of patients showing synovial thickening, joint effusion, meniscus tear, synovial enhancement, osteophytes. A point estimate and 95% confidence interval will be provided for each secondary outcome at each time and for the change in each outcome from baseline to each post-treatment follow-up visit. Changes in the outcomes from baseline to follow-up will be tested using the paired-sample Wilcoxon signed rank test for the WOMAC and VAS scores and the McNemar test for the other measures which will be assessed as binary outcomes (e.g., whether or not the patient reported usage of pain medication on a daily basis).

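### The only analysis dataset is completers of all follow-up visits, so the adverse event and technical success rates have no denominator that keeps every treated patient

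*Combined protocol and SAP*

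**What the plan says.** All references are to the combined protocol and SAP.

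- **Dataset.** Section 10.3 (Analysis Datasets) is one sentence: "Participants who complete all follow-up visits will be included in the study". No safety, treated or attempted-procedure set is defined anywhere, and Section 10.1 says no formal SAP will be produced before database lock.
- **AE rate.** Section 10.4.4: "Safety endpoints will assess adverse event rate (defined as the proportion of patients showing each type of adverse event or any adverse event". Section 10.4.3 repeats the definition. The related objective in Section 3.2 reads: "Safety evaluated by cumulative rates of adverse events (AE), as well as type and severity of each adverse event". None of the three names a denominator.
- **Technical success.** Section 10.4.3 lists "the technical success rate (defined as the proportion of patients for whom the procedure was successfully completed". Section 3.2 defines it differently, as selective catheterization plus embolization from at least one artery feeding the joint.
- **Withdrawal and replacement.** Section 5.7.1 lists among the reasons for discontinuation "Any AE, clinically significant adverse event, severe laboratory abnormality, intercurrent illness, or other medical condition" that makes continued participation, in the investigator's view, not in the patient's interest. Section 5.7.2 adds: "Withdrawn patients can be replaced". It does not limit replacement to patients who have not yet been treated.

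**The concern.** Whether a patient completes all visits is settled after treatment and can depend on what the treatment did. If the AE rate is computed only among completers, a patient whose AE ends participation leaves both the numerator and the denominator, and a replacement may fill the place. Death is the clearest case. It is the top severity category in Section 8.2.1, and a patient who dies before month 12 cannot be a completer.

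Technical success raises a related problem. The result is known at the end of the Day 0 procedure, so there is no reason to make it depend on attendance a year later.

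Section 4.1 describes the study as designed to evaluate safety and feasibility. The two summary rates that answer those questions are the ones affected.

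**Working it through.** **1. The plan's own figures.** Sections 5.6 and 10.5 give 40 patients with data, 20% attrition and 50 accrued: 40 / (1 − 0.20) = 50. The initial size also reproduces: 23 / 0.80 = 28.75, rounded up to 29. The exact one-sided binomial rule of at least 16 of 23 has a significance level of 0.0466 under a true proportion of 0.5 and power 0.8037 under 0.75, against the stated 0.047 and 80.4%. These figures do not bear on the denominator question; they only supply the split of 40 and 10.

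**2. Assumptions.** The documents do not say how events divide between completers and non-completers. I assume that all 50 accrued patients are treated, that 40 complete, and that follow-up ends at month 12 (Visit 8 is optional). Let c be the number of completers with an AE and d the number among the 10 non-completers.

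- Completer rate = c/40
- All-treated rate = (c + d)/50
- Difference (all-treated minus completer) = d/50 − c/200

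The completer rate is too low when d > c/4 and too high when d < c/4.

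**3. AE rate, with Clopper-Pearson 95% intervals.**

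| c | d | Completer rate | All-treated rate |
|---|---|---|---|
| 2 | 0 | 2/40 = 5.0% (0.6 to 16.9) | 2/50 = 4% (0.5 to 13.7) |
| 2 | 3 | 5.0%, unchanged | 5/50 = 10% (3.3 to 21.8) |
| 2 | 10 | 5.0%, unchanged | 12/50 = 24% (13.1 to 38.2) |
| 0 | 0 | 0/40 = 0% (upper limit 8.8) | 0/50 = 0% (upper limit 7.1) |
| 0 | 10 | 0%, unchanged | 10/50 = 20% (10.0 to 33.7) |

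The completer figure does not respond to anything that happens in the other 10 patients. With c = 2, c/4 = 0.5, so a single affected non-completer (3/50 = 6%) already makes 5.0% an understatement.

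**4. If some attrition precedes treatment.** Section 5.7.1 includes an exit for osteonecrosis on the pre-procedural MRI, so not all 10 need be treated. If 45 are treated and 5 of them do not complete, then with c = 2 the all-treated rate runs from 2/45 = 4.4% to 7/45 = 15.6%. The range narrows but does not close.

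**5. Technical success.** If all 40 completers were successes, the completer rate is 40/40 = 100% (91.2 to 100). Over all attempted procedures it is 50/50 = 100% (92.9 to 100), 47/50 = 94% (83.5 to 98.7) or 40/50 = 80% (66.3 to 90.0) if 0, 3 or 10 non-completers were failures. If 3 failed cases instead attend every visit and the other 47 procedures succeed, the completer rate is 37/40 = 92.5% against 47/50 = 94%, and the error runs the other way.

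**The case against.** **The events are not lost.** For patients who withdraw, Section 5.7.2 says "study staff should make every effort to complete the full panel of assessments scheduled for the follow-up visits" and asks that their AEs be captured. Sections 8.3 and 8.4.2 require on-study AEs to be recorded and followed, with serious events captured to 30 days after the last visit. Reporting to the sponsor and the FDA (Sections 8.5 and 8.6) and the halting rule (Section 8.7) are not limited to completers. All of this stands. A reader might infer that safety oversight under the IDE is compromised; the documents do not support that. But these are rules for collection and reporting, and none of them places withdrawn patients in the Section 10.4.4 rate.

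**Section 10.3 speaks of inclusion in the study, not in every analysis.** The rates are defined over patients, Section 3.2 promises cumulative AE rates, and Section 10.4.4 grades all AEs. This stands in part: the plan nowhere announces that harmed patients will be dropped, and it should not be read as intending that. Even so, the sentence sits under the Analysis Datasets heading, no other set exists, and no SAP will follow to correct the literal reading.

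**An AE need not end participation.** Treatment is a single session and discontinuation under Section 5.7.1 is discretionary, so many patients with an AE may complete. This limits the size of the problem. It does not help with death or with a patient who is discontinued and replaced.

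**This is a pilot with descriptive safety summaries.** That is so, but a descriptive rate still needs a denominator that the outcome cannot alter.

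**Conclusion.** The concern holds for the summary rates. Section 10.3 supplies one dataset, completers, and Sections 10.4.3 and 10.4.4 give no alternative. Taken literally, the AE rate omits treated patients who die before month 12 or who are discontinued for an AE, and technical success depends on later attendance.

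Up to 10 of 50 patients can fall outside both rates, which can move either rate by up to 20 percentage points. That figure assumes all 50 are treated and takes the extreme split; the event splits shown are assumptions, not forecasts.

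Two stronger readings are tempting and are not supported:

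- *That the AE rate must be understated.* The direction depends on the split: 2/40 = 5% exceeds 2/50 = 4% when no non-completer is affected. Withdrawal caused by AEs pushes towards understatement, but the documents do not fix the sign.
- *That technical success is bound to reach 100%.* A failed procedure is not a listed reason for withdrawal in Section 5.7.1, and nothing says such patients leave. One who attends every visit is a completer and counts as a failure.

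**What to change.** Before database lock:

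1. Add to Section 10.3 a safety and feasibility set of every patient in whom the procedure was attempted, defined by arterial access. State that withdrawn and replaced patients remain in it.
2. In Sections 10.4.3 and 10.4.4, use this set as the denominator for all AE rates and for technical success.
3. Use the Section 3.2 definition of technical success in Section 10.4.3 so that the two agree, and state in advance how a patient with no abnormal vessels at angiography is counted, since that definition presupposes a target vessel.
4. Section 10.4.3 already promises 95% confidence intervals for secondary outcomes; specify that those for these rates are exact.
5. Section 8.3 records events from consent, so list AEs between consent and arterial access separately.

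The cost is a few sentences. No new data are needed, because the procedure result is known on Day 0 and the protocol already requires AEs to be captured in patients who withdraw.

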10.5 Sample Size

The sample size was initially selected based on primary objective so that the study will have 80% power at the 5% significance level for testing the null hypothesis H_0 : $PT \leq 0.5$ against the alternative hypothesis H_A : $PT \geq 0.75$, where PT is the true proportion of patients that will manifest a positive treatment response. As a result, the study will accrue 23 patients since this sample size will endow the test with 80.4% power at a realized significance level of 0.047. with 20% attrition, the study will need 29 patients. We are requesting increase in the sample size to 40. With 20% with 20% attrition, the study will need to enroll 50 patients. The PI and sub-investigators determined that increase in the sample size is necessary to

CONFIDENTIAL

evaluate the role of GAE as a disease-modifying treatment option for knee OA. Since this current study is the only active study in the U.S collecting samples for biomarker analysis and the need for a larger sample size to evaluate changes in biomarker levels, an increase in sample size is needed.

11 Source Documents and Access to Source Data/Documents

Source data is all information, original records of clinical findings, observations, or other activities in a clinical trial necessary for the reconstruction and evaluation of the trial. Source data are contained in source documents. Examples of these original documents, and data records include: hospital records, clinical and office charts, laboratory notes, memoranda, subjects' diaries or evaluation checklists, pharmacy dispensing records, recorded data from automated instruments, copies or transcriptions certified after verification as being accurate and complete, microfiches, photographic negatives, microfilm or magnetic media, x-rays, subject files, and records kept at the pharmacy, at the laboratories, and at medical-technical departments involved in the clinical trial. It is acceptable to use CRFs as source documents. Data collected on electronic CRFs using TrialMaster are attached to this protocol (see attachment 4).

The study case report form (CRF) is the primary data collection instrument for the study. All data requested on the CRF must be recorded. All missing data must be explained. If a space on the CRF is left blank because the procedure was not done or the question was not asked, write "N/D". If the item is not applicable to the individual case, write "N/A". All entries should be printed legibly in black ink. If any entry error has been made, to correct such an error, draw a single straight line through the incorrect entry and enter the correct data above it. All such changes must be initialed and dated. **DO NOT ERASE OR WHITE OUT ERRORS.** For clarification of illegible or uncertain entries, print the clarification above the item, then initial and date it.

Access to study records will be limited to IRB-approved members of the study team. The investigator will permit study-related monitoring, audits, and inspections by the IRB/EC, the sponsor, government regulatory bodies, and University compliance and quality assurance groups of all study related documents (e.g. source documents, regulatory documents, data collection instruments, study data etc.). The investigator will ensure the capability for inspections of applicable study-related facilities (e.g. pharmacy, diagnostic laboratory, etc.).

Participation as an investigator in this study implies acceptance of potential inspection by government regulatory authorities and applicable University compliance and quality assurance offices.

12 Quality Assurance and Quality Control

QC procedures will be implemented beginning with the data entry system and data QC checks that will be run on the database will be generated. Any missing data or data anomalies will be communicated for clarification/resolution.

The PI will verify that the clinical trial is conducted and data are generated, documented (recorded), and reported in compliance with the protocol, GCP, and the applicable regulatory requirements (e.g., Good Laboratory Practices (GLP), Good Manufacturing Practices (GMP)).

The investigational site will provide direct access to all trial related sites, source data/documents, and reports for the purpose of monitoring and auditing by the sponsor, and inspection by local and regulatory authorities.

CONFIDENTIAL

This material is the property of the NYU School of Medicine and Langone Medical Center. Do not disclose or use except as authorized in writing by the study sponsor
Interventional Template Version: 12 February 2020

13 Ethics/Protection of Human Subjects

13.1 Ethical Standard

All investigators will ensure that this study is conducted in full conformity with Regulations for the Protection of Human Subjects of Research codified in 45 CFR Part 46, 21 CFR Part 50, 21 CFR Part 56, and/or the ICH E6.

13.2 Institutional Review Board

The protocol, informed consent form(s), recruitment materials, and all participant materials will be submitted to the IRB for review and approval. Approval of both the protocol and the consent form must be obtained before any participant is enrolled. Any amendment to the protocol will require review and approval by the IRB before the changes are implemented to the study. All changes to the consent form will be IRB approved; a determination will be made regarding whether previously consented participants need to be re-consented.

13.3 Informed Consent Process

13.3.1 Consent/Assent and Other Informational Documents Provided to Participants

Consent forms describing in detail the study agent, study procedures, and risks are given to the participant and written documentation of informed consent is required prior to starting intervention/administering study product. The consent form is submitted with this protocol (See attachment 9).

13.3.2 Consent Procedures and Documentation

Informed consent is a process that is initiated prior to the individual's agreeing to participate in the study and continues throughout the individual's study participation. Extensive discussion of risks and possible benefits of participation will be provided to the participants and their families. Consent forms will be IRB approved and the participant will be asked to read and review the document. The investigator will explain the research study to the participant and answer any questions that may arise. All participants will receive a verbal explanation in terms suited to their comprehension of the purposes, procedures, and potential risks of the study and of their rights as research participants. Participants will have the opportunity to carefully review the written consent form and ask questions prior to signing. The participants should have the opportunity to discuss the study with their surrogates or think about it prior to agreeing to participate. The participant will sign the informed consent document prior to any procedures being done specifically for the study. The participants may withdraw consent at any time throughout the course of the trial. A copy of the signed informed consent document will be given to the participants for their records. The rights and welfare of the participants will be protected by emphasizing to them that the quality of their medical care will not be adversely affected if they decline to participate in this study.

A copy of the signed informed consent document will be stored in the subject's research record. The consent process, including the name of the individual obtaining consent, will be thoroughly documented in the subject's research record. Any alteration to the standard consent process (e.g. use of a translator, consent from a legally authorized representative, consent document presented orally, etc.) and the justification for such alteration will likewise be documented.

CONFIDENTIAL

13.4 Participant and Data Confidentiality

Information about study subjects will be kept confidential and managed according to the requirements of the Health Insurance Portability and Accountability Act of 1996 (HIPAA). Those regulations require a signed subject authorization informing the subject of the following:

- What protected health information (PHI) will be collected from subjects in this study
- Who will have access to that information and why
- Who will use or disclose that information
- The rights of a research subject to revoke their authorization for use of their PHI.

In the event that a subject revokes authorization to collect or use PHI, the investigator, by regulation, retains the ability to use all information collected prior to the revocation of subject authorization. For subjects that have revoked authorization to collect or use PHI, attempts should be made to obtain permission to collect at least vital status (i.e. that the subject is alive) at the end of their scheduled study period.

Participant confidentiality is strictly held in trust by the participating investigators, their staff, and the sponsor(s) and their agents. This confidentiality is extended to cover testing of biological samples and genetic tests in addition to the clinical information relating to participants. Therefore, the study protocol, documentation, data, and all other information generated will be held in strict confidence. No information concerning the study or the data will be released to any unauthorized third party without prior written approval of the sponsor.

The study monitor, other authorized representatives of the sponsor, representatives of the IRB or pharmaceutical company supplying study product may inspect all documents and records required to be maintained by the investigator, including but not limited to, medical records (office, clinic, or hospital) and pharmacy records for the participants in this study. The clinical study site will permit access to such records.

The study participant's contact information will be securely stored at each clinical site for internal use during the study. At the end of the study, all records will continue to be kept in a secure location for as long a period as dictated by local IRB and Institutional regulations.

Study participant research data, which is for purposes of statistical analysis and scientific reporting, will be transmitted to and stored at NYU Langone Health. This will not include the participant's contact or identifying information. Rather, individual participants and their research data will be identified by a unique study identification number. The study data entry and study management systems used by NYU Langone Health research staff will be the Institution-approved, encrypted and HIPAA-compliant version of TrialMaster managed by MCIT. At the end of the study, all study databases will be de-identified and archived at the NYU Langone Health.

